Conflict of interest declaration

None declared.

SUMMARY

Background: Overweight is a main and modifiable risk factor for developing knee osteoarthritis (OA). Studies indicate a beneficial effect of weight loss on the symptoms of knee OA. The Intensive diet vs Knee Arthroplasty (INKA) trial is a RCT, which aims to assess weight loss as a non-inferior intervention and/or an alternative to surgical knee arthroplasty in overweight and obese patients suffering from knee OA. As RCTs carry a risk for selection bias and thereby risk for low external validity, comparison of the recruited trial participants and the invited participants, who decline trial participation will enable assessment of the external clinical validity and generalizability of the INKA trial

Objective: The objective of this study is to compare baseline characteristics of overweight knee OA patients accepting vs. declining enrolment in the INKA trial to explore if enrolled patients differ systematically from the declining participants with respect to both measured as well as unmeasured baseline characteristics.

Design: Cross-sectional study collecting baseline characteristics of patients with Knee OA eligible for enrolment in the INKA trial, whether accepting or declining enrolment.

Setting: Potential trial participants will be identified during their routine visits in the orthopaedic outpatient clinics at Copenhagen University Hospital Bispebjerg-Frederiksberg and Copenhagen University Hospital Amager-Hvidovre.

Participants: Adults ≥ 18 years old, obese ($BMI \geq 30 \text{ kg/m}^2$), with an indication for primary knee arthroplasty (unicondylar or total arthroplasty) due to knee OA are included either with consent or refusal to participation in the INKA trial. We will recruit 400 patients in total, 200 in each group.

Measurements: Baseline characteristics for the 2 groups are obtained extracting data from the participants' medical records including questionnaires answered by all patients, of which the main is The Oxford Knee Score (the primary outcome for INKA participants).

Data synthesis: We will use standardized difference of the mean (or medians) of continuous variables or the prevalence of dichotomous baseline covariates between INKA and nINKA participants. A standardized difference of ≥ 0.2 to indicate that there might be a meaningful imbalance in the baseline covariate, whereas a standardized difference ≥ 0.8 will be considered as definitive incomparability. We will also apply the PROC NPAR1WAY procedure (using SAS software) to compute empirical distribution function (EDF) statistics. Finally, we will do a logistic regression to calculate propensity scores to represent the probability that a consent to participation is based on observed covariates.

Registration: This protocol will be registered with ClinicalTrials.gov before recruiting the participants. Data management (storage, analysis, backup and deletion) will be consistent with standard procedures of Region Hovedstaden.

1.0 INTRODUCTION

Osteoarthritis (OA) is the most common joint disorder in the world, with a prevalence of around 16% for individuals aged ≥ 15 years, and around 23% for individuals older than 39 years old worldwide. It is found as a leading cause for disability and loss of function with huge costs to the society through lost workdays, early retirement and direct treatment costs (1,2). Knee OA stands for 83% of all OA localizations, with 250 million cases worldwide (3). Many risk factors, like increasing age, acute joint injury, joint deformity and overweight have been identified, where overweight is considered to be a main risk factor for developing knee OA (1,4). The treatment of knee OA is a multi-step process, that starts with physiotherapy, weight loss, non-pharmacological treatment and simple medical treatment as step one, advanced pharmacological treatment as step 2, a last pharmacological attempt on the third step, and ends with joint replacement for the end stage disease if not contra-indicated (5). Given the fact that the obesity is a modifiable risk factor, weight loss is an important part of the treatment strategy of knee OA (5,6). A weight reduction of over 5.1% bodyweight within 20-weeks period is found to significantly improve disability in a systematic review and meta-analysis from 2007 (7). A more recent randomized, 2-phase, parallel-group trial found that a mean 10% weight reduction with a 1-year weight maintenance program improves symptoms in patients with knee OA and a subsequent long term follow-up showed that the use of daily meal replacements or intermittent low-energy diet maintained weight reduction for 3 years (8,9). In the pursuit of reducing the incidence of joint replacement surgery, a cohort study from Australia suggests that the risk of total knee replacement (TKR) can be reduced with weight loss of $>7.5\%$ of body weight in adults with overweight or obesity, but no such correlation could be found for total hip replacement (THR) (10). Furthermore, a weight reduction of 10% before TKR surgery is found to improve the general health-related outcomes one year after TKR (11).

The INTensive diet vs Knee Arthroplasty (INKA) trial is a RCT, which aims to assess weight loss as a non-inferior intervention and/or an alternative to surgical knee arthroplasty in overweight and obese patients suffering from knee OA. The INKA study carries by the nature design of a RCT a high internal validity. The external validity of the trial is important to know to convince professionals to change the treatment strategy, as it reflects the generalizability of the trial results.

2.0 RATIONALE

Many systematic reviews of published articles have found a tendency of poor representativeness of external validity (12–15). To interpret the generalizability of a RCT, evaluation of excluded and declining patients is of importance. In the INKA trial, we may speculate that those declining inclusion have a more severe knee problem whereas those who are included may be more concerned about having knee surgery. A comparison of the recruited trial participants and the invited participants, who decline trial participation on a range of clinical, para-clinical, and phenotypical variables will enable assessment of the external clinical validity and generalizability of the INKA trial, which will strengthen the usefulness and relevance of the INKA trial results.

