4.3 Participants

All patients found eligible in INKA study (inclusion criteria for INKA) and accepting and declining enrolment in the INKA study are invited to participate in our study. We report the number of patients assessed for eligibility and reasons of exclusion. Study participants will be adults (i.e. at

least 18 years old), have a diagnosis of knee osteoarthritis with an indication for primary knee arthroplasty (unicondylar or total arthroplasty), and be obese ($BMI \geq 30 \text{ kg/m}^2$). An individual will be eligible for study participation if he/she meets the following criteria:

1. Age 18 or more
2. A clinical and radiological diagnosis of knee OA
3. $BMI \geq 30 \text{ kg/m}^2$
4. Motivated for weight loss as by the provided program
5. Signed informed consent.

A possible participant will, however, be excluded from the study if he/she meets any of the following criteria:

1. The scheduled surgery is for revision of an existing prosthesis
2. Planned surgery for more than one knee within the observation period
3. KA indication due to sequelae of fracture(s)
4. Injection of medication or substances in the target knee within 3 months prior to participation
5. Immuno-inflammatory arthritis as cause of the knee OA
6. Current systemic treatment with glucocorticoids equivalent to $> 7.5 \text{ mg}$ of prednisolone/day
7. Previous or planned obesity surgery
8. Inability to understand or read Danish incl. instructions and questionnaires
9. Any other condition or impairment that, in the opinion of the investigator (or his/her delegate), makes a potential participant unsuitable for participation or which obstruct participation.

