4.4 Variables

The following variables will be assessed at baseline independent of their acceptance to participate in the INKA Trial

1. Age
2. Sex
3. Disease duration

4. Height (meters)
5. Body weight (kg)
6. Type of scheduled arthroplasty (Total vs Unicdylar prosthesis)
7. The Oxford Knee Score (OKS)
8. Health outcome and quality of life survey (EuroQoL questionnaire)
9. Use of analgesics
10. The Knee injury and Osteoarthritis Outcome Score (KOOS) – 12 item short form
11. Patient’s global assessment of impact of the knee in daily life (PGA)
12. Illness perception questionnaire

Table 1: Collected baseline characteristics

Characteristics	Patients accepting INKA group	Patients declining nINKA group	Standardised Difference
Total, no. (%)			
Age, year			
Gender:			
Females, no. (%)			
Males, no. (%)			
Disease duration, years			
Height, meters			
Weight, kg			
Type of scheduled arthroplasty:			
Total knee arthroplasty, no. (%)			
Unicdylar knee arthroplasty, no. (%)			
The Oxford Knee Score (OKS)			
EuroQoL Index			
EuroQoL VAS			
Regular use of analgesics no. (%)			
Paracetamol/acetaminophen			
NSAIDs			
Acetylic acids			
Opiods			
The Knee injury and Osteoarthritis Outcome Score (KOOS) – 12 item short form:			

Pain score			
Function score			
QoL score			
Patient's global assessment of impact of the knee in daily life (PGA)			
Illness perception questionnaire:			
Item 1, score			
Item 2, score			
Item 3, score			
Item 4, score			
Item 5, score			
Item 6, score			
Item 7, score			
Item 8, score			

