4.5 Data sources/measurements

4.5.1 The Oxford Knee Score (Primary Outcome)

The Oxford Knee Score (OKS) is a 12-item Patient Reported Outcome questionnaire developed specifically to assess the patient's perspective on the outcomes of knee arthroplasty (KA) with respect to combined pain and physical function. Standardized answer options are given (5 Likert boxes) and each question is assigned a score from 0 to 4. Thus, a total score is calculated that ranges from 0 and 48, with 48 indicating the best outcome. The OKS is short, practical, reliable, valid, and sensitive to clinically important changes over time (16).

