4.6.3 Brief Illness perception questionnaire (B-IPQ)

B-IPQ is a generic 9-item questionnaire developed to rapidly assess the cognitive and emotional representations in a variety of illnesses. B-IPQ is a short version of the 84-item revised illness perception questionnaire (IPQ-R) (21). B-IPQ assesses perceptions on the following five

dimensions: Identity, Cause, Timeline, Consequences and Cure-Control. Five of the items assess cognitive illness representations; two of the items assess emotional representations; and one item assesses illness comprehensibility. The ninth item is a free text field in which the respondent can formulate their beliefs about their condition (cause). We will not use this field in our study.

The first 8 items are scored on a 0-3 Likert scale with descriptors (none or extreme) at either end. The B-IPO scores have shown good test-retest reliability and adequate concurrent, discriminative, and predictive validity amongst patient samples with musculoskeletal disorders and other chronic disorders (22,23).

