4.8 Bias and confounding variables

Confounding is an important concept in epidemiology, because, if presents, it can cause an over- or underestimate of the observed association between exposure and health outcome. The distortion introduced by a confounding factor can be large, and it can even change the apparent direction of an effect. However, unlike selection and information bias, it can be adjusted for in the analysis.

The challenge with observational data (like the proposed comparison) is that the groups (INKA vs nINKA) are not applied randomly, leading to selection bias and thus potentially confounding variables. For example, when we study the impact entering a “promising weight loss trial” before having direct access to a KA, and we compare the outcome among those (who accept the invitation to join the INKA trial) versus all of those who declined, we would potentially have some selection bias, as those who decline are different per definition. The difference can range from baseline characteristics that would influence the outcome; i.e., an advanced disease stage that make any potential delay of the surgery intolerable, or failure/ineffectiveness of previous weight loss trials. Or it can be a characteristic with neglectable effect on the outcome, ie., not having the time or the desire to be included in a clinical trial. Improved confounding variable balance (i.e. de-confounding) between INKA and nINKA groups can be achieved by matching observations from each group based on the propensity score, which in this case would be the probability that a patient accept participation in INKA given the observed covariates.

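### Section 2.0 promises para-clinical variables and sections 2.0 and 4.8 name possible differences between acceptors and decliners, but Table 1 has no para-clinical variable, no weight-loss history and no attitude to surgery

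*Combined protocol and SAP*

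**What the plan says.** Section 2.0 (Rationale) states that comparing those recruited with those "who decline trial participation on a range of clinical, para-clinical, and phenotypical variables will enable assessment of the external clinical validity". The same section speculates that "those declining inclusion have a more severe knee problem whereas those who are included may be more concerned about having knee surgery".

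Section 4.8 describes how the groups might differ. As examples of characteristics that would bear on outcome it gives "an advanced disease stage that make any potential delay of the surgery intolerable, or failure/ineffectiveness of previous weight loss trials". It then gives examples with little bearing on outcome, such as having no time for a trial.

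Section 4.4 opens its list with "The following variables will be assessed at baseline independent of their acceptance to participate in the INKA Trial", and Table 1 sets out the comparison. The entries are demographics, disease duration, height, weight, planned prosthesis type, analgesic use and patient-reported scores. Imaging appears only in section 4.3, where entry criterion 2 is "A clinical and radiological diagnosis of knee OA".

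**The concern.** The rationale and the variable list do not match. One class of variable promised in section 2.0 is absent from section 4.4, and factors that the authors themselves suggest may separate the groups have no row, or only an indirect one.

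This matters because the study exists to say how far INKA's results carry over to eligible patients who decline. Section 4.9 treats the crude comparisons as indicative of generalizability, and builds the propensity score only from baseline variables that are collected. A reader who sees small standardized differences in every row would learn nothing direct about weight-loss history or attitude to surgery. Weight-loss history is the clearest gap: the parent trial tests a weight-loss programme, and section 4.8 says earlier failure would influence outcome.

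**Working it through.** This is a check of coverage. No figure in the plan bears on it; the power figures in the note to section 4.7 concern the parent trial.

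**Step 1. Count what Table 1 compares.** Age 1, sex 1, disease duration 1, height 1, weight 1, prosthesis type 1, OKS 1, EuroQoL index and VAS 2, analgesic classes 4, KOOS-12 scales 3, PGA 1, B-IPQ items 8. The sum is 6 + 1 + 2 + 4 + 3 + 1 + 8 = 25.

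**Step 2. Set each promised or named factor against those 25.** The plan does not define para-clinical; I take it to mean imaging, laboratory or similar test results.

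| Factor | Where named | Direct rows | Nearest proxy |
|---|---|---|---|
| Para-clinical variables | 2.0 | 0 | none |
| More severe knee problem | 2.0 | covered at symptom level | OKS, KOOS-12, PGA, analgesics |
| Advanced disease stage | 4.8 | 0 | the same symptom measures; disease duration; prosthesis type |
| Failed earlier weight loss | 4.8 | 0 | none |
| Concern about surgery | 2.0 | 0 | at most weak: B-IPQ |

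**Step 3. Check the proxies.** Section 4.5.1 describes the OKS as assessing the patient's perspective "with respect to combined pain and physical function", so it records symptoms. Section 4.6.3 says of the B-IPQ that "two of the items assess emotional representations", but describes these as perceptions of the illness; the operation is not mentioned. The Timed Up and Go is mentioned in section 4.9 only as an illustration of units and is in neither section 4.4 nor Table 1.

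**Step 4. Ask whether the analysis can recover the gap.** A standardized difference needs the variable in both groups. The propensity model in section 4.9 takes only collected variables. Neither can show imbalance on a factor with no row, except as far as a listed proxy carries it. Section 4.3 reports reasons for exclusion but does not mention reasons for declining. Such reasons would in any case come from one group only and would give no comparison.

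**The case against.** The strongest reply is that the plan claims less than a critic might make it claim. Four readings are tempting, and the documents support none of them.

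- A reader might infer that the plan ranks these factors as the likeliest to separate the groups. It does not. Section 2.0 speculates and section 4.8 lists examples.
- A reader might infer that the plan says structural differences affect outcome. It does not mention structural or radiographic stage. Section 4.8 ties advanced stage to delay being intolerable, which pain and function may largely reflect, and those are measured.
- A reader might infer that balance on every row would be declared good generalizability. No such rule is written. A standardized difference of 0.2 or more is a warning of imbalance; the converse is not stated.
- A reader might infer that a hidden imbalance in stage would slip under the 0.2 flag. That depends wholly on assumed inputs. With the section 4.9 formula, 60% against 40% gives 0.20/√0.24 = 0.41 in size, and a proxy correlated 0.4 with stage would show 0.41 × 0.4 = 0.16. But 65% against 35% gives 0.30/√0.2275 = 0.63, and 0.63 × 0.4 = 0.25, above the flag. The documents give neither the split nor the correlation.

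There is also some partial coverage. Section 4.3 requires motivation for weight loss and excludes previous or planned obesity surgery, which narrows the weight-loss background. The B-IPQ includes a cure-control dimension. The questionnaires and screening log are appendices that are not available here, and may hold relevant items.

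These points limit the concern but leave the mismatch standing. Nothing in section 4.3 records whether earlier weight-loss attempts failed, and whatever the appendices contain, section 4.4 and Table 1 plan no comparison of it.

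**Conclusion.** The mismatch holds in a limited form. Of 25 comparisons, none is para-clinical, none records weight-loss history and none records attitude to surgery. Disease stage is covered at symptom level and by indirect proxies only. Balance or imbalance on these factors cannot be shown directly, and balance on Table 1 would say nothing about weight-loss history in particular.

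The conclusion rests on section 4.4 and Table 1 being the complete list of compared variables, and on the ordinary meaning of para-clinical. It does not rest on any assumed prevalence or correlation, and the size of any resulting misjudgement cannot be calculated from the documents. No planned analysis is invalid. The study can run as written, but with a narrower reach than section 2.0 promises.

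**What to change.** Add two variables to section 4.4, Table 1 and the propensity model, for both groups:

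- (a) a previous structured weight-loss attempt and whether it failed, as yes/no, with failure defined in the protocol;
- (b) radiographic severity where it is already stated in the record used for entry criterion 2, with no new imaging or reading.

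An entry diagnosis does not guarantee that a grade was written down. Report how many grades are missing in each group, and say how those patients enter the propensity model, since a complete-case fit would drop them. If (b) is too rarely recorded to use, delete the word para-clinical from section 2.0 and state that structural severity was not compared.

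An item on concern about surgery is optional. Use it only if it is answered before the participation decision; afterwards the answer may reflect the decision instead of explaining it. If it is left out, say so as a limitation.

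The cost is one field from records already being extracted, a slightly longer questionnaire and some missing grades.

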3.0 OBJECTIVE(S)

The objective of this study is to compare baseline characteristics of overweight knee OA patients accepting vs. declining enrolment in the INKA trial, in order to explore if the enrolled patients differ systematically from the declining participants in both measured as well as unmeasured baseline characteristics.

4.0 METHODS

4.1 Study design

The INKA trial is designed as a pragmatic, randomized, parallel-group trial. The trial is designed to compare the effectiveness of a supervised weight loss program to surgical knee arthroplasty in obese individuals with knee OA.

We will use a cross-sectional study design collecting baseline characteristics of patients with knee OA eligible for enrolment in the INKA trial, accepting or declining enrolment in the clinical trial, while recruiting patients for the trial. Data collection starts on the 01.01.2022 and ends with the inclusion of the last patient in INKA study (i.e. anticipated: 01-06-2023) Figure 1.

[figure not shown]

Figure 1- study flow chart

4.2 Setting

Potential trial participants will be identified by an investigator or his/her delegate in the orthopaedic outpatient clinics at Copenhagen University Hospital Bispebjerg-Frederiksberg and Copenhagen University Hospital Amager-Hvidovre. The identification of potential participants may occur during regular clinical visits.

4.3 Participants

All patients found eligible in INKA study (inclusion criteria for INKA) and accepting and declining enrolment in the INKA study are invited to participate in our study. We report the number of patients assessed for eligibility and reasons of exclusion. Study participants will be adults (i.e. at

least 18 years old), have a diagnosis of knee osteoarthritis with an indication for primary knee arthroplasty (unicondylar or total arthroplasty), and be obese ($BMI \geq 30 \text{ kg/m}^2$). An individual will be eligible for study participation if he/she meets the following criteria:

1. Age 18 or more
2. A clinical and radiological diagnosis of knee OA
3. $BMI \geq 30 \text{ kg/m}^2$
4. Motivated for weight loss as by the provided program
5. Signed informed consent.

A possible participant will, however, be excluded from the study if he/she meets any of the following criteria:

1. The scheduled surgery is for revision of an existing prosthesis
2. Planned surgery for more than one knee within the observation period
3. KA indication due to sequelae of fracture(s)
4. Injection of medication or substances in the target knee within 3 months prior to participation
5. Immuno-inflammatory arthritis as cause of the knee OA
6. Current systemic treatment with glucocorticoids equivalent to $> 7.5 \text{ mg}$ of prednisolone/day
7. Previous or planned obesity surgery
8. Inability to understand or read Danish incl. instructions and questionnaires
9. Any other condition or impairment that, in the opinion of the investigator (or his/her delegate), makes a potential participant unsuitable for participation or which obstruct participation.

